Comparative Study of advance platelet rich fibrin/concentrated growth factor technology in regenerative periodontal surgery: a randomized controlled clinical trial

I. background

Periodontitis is one of the most common oral diseases, which is characterized by alveolar bone resorption and destruction. Severe periodontitis has become the sixth largest epidemic disease in the world, and it is the leading cause and main cause of tooth loss in adults. As a major country in the incidence of periodontitis, there is a huge population of patients with severe periodontitis in China, and the incidence rate is as high as 12.1-16.1%. The ideal treatment of periodontitis is not only to eliminate pathogenic factors and control inflammation, but also to reconstruct and repair the damaged periodontal tissue structure and achieve periodontal tissue regeneration so as to preserve natural teeth for a long time.

At present, guided tissue regeneration (GTR) combined with bone grafting is the main method for clinical treatment of periodontal bone defects. This classical operation uses membranous materials to shield the faster growing gingival epithelial cells and connective tissue cells to create an effective closed space and time for the growth of periodontal ligament cells with regenerative potential. as a result, new cementum is formed on the root surface and periodontal ligament fibers are embedded, resulting in regenerative healing. At the same time, the bone graft material was implanted into the periodontal tissue defect area to maintain enough submembrane space to help stabilize the blood clot which is essential for

periodontal regeneration, and then guide the formation of autogenous bone tissue. However, it has been reported that although GTR can repair intraosseous defects to a certain extent, the results of periodontal tissue restoration are far from achieving the desired goals of doctors and patients. At the same time, according to the 2015 consensus of the American periodontal Association on the treatment of periodontal bone defect regeneration, the existing indications of regeneration surgery are limited to narrow and deep subosseous pockets, according to this requirement, the shape and depth of most bone defects do not have the conditions for regeneration surgery, or even if the regeneration operation is performed, the effect of the operation is very limited, and the affected teeth can only be extracted in the end.

In order to improve the effect of periodontal regeneration therapy, scholars try to combine platelet concentrate containing a variety of growth factors with bone grafts in periodontal regenerative surgery to improve the ability of local bone induction and tissue healing. Among them, the latest generation of autologous platelet concentrate, modified platelet-rich fibrin (APRF), contains rich autologous growth factors that promote cell proliferation and migration, which can promote new angiogenesis, wound healing and accelerate tissue remodeling. Studies have shown that gel-like APRF contains collagen fibers close to the physiological state, which can provide an effective three-dimensional scaffold for cell proliferation, as a natural vascularization-inducing component and immune response support. Among them, TGF- β , VEGF and other growth factors can

promote angiogenesis, inhibit osteoclasts, facilitate the migration and proliferation of gingival fibroblasts, and provide a good microenvironment for the repair and regeneration of traumatic tissue. On the other hand, in 2006, Sacco et al used inner wall coating test tube with silica, concentrated growth factor (CGF) was prepared after differential centrifugation. CGF uses differential centrifugation technology, so the fibrin clot obtained is larger than platelet-rich fibrin (PRF), and the content of fibrin is more. The three-dimensional fibrin network structure of CGF can be observed under scanning electron microscope, red blood cells and platelets are fixed in the fiber network, and the fiber of CGF is thicker and more regular than PRF. The contents and release rules of key growth factors in APRF/CGF were compared, and it was found that both APRF and CGF could stably release higher concentrations of growth factors PDGF- α β , TGF- β and VEGF, while APRF released more and more sustained growth factors than CGF in the later stage, suggesting that APRF may have better structure and function of promoting tissue repair and regeneration than CGF. However, there is no significant difference in the efficacy of APRF and CGF platelet concentrates in periodontal regeneration surgery, and there are some defects such as low level of evidence, small number of case samples, short observation period and so on. At present, there are still few studies on the application of the two in the treatment of clinical periodontal tissue regeneration, and there is no report on comparing the clinical effects of the two through randomized clinical controlled trials.

Based on this, this study compares the clinical application of GTR combined

with APRF/CGF and simple GTR in promoting periodontal bone defect regeneration through randomized clinical controlled trials, and intends to further explore the efficacy of the three methods in improving the amount of alveolar bone regeneration, so as to provide a certain basis for future clinical work.

II. The purpose of the clinical trial

The purpose of this study is to compare the clinical application of GTR combined with APRF/CGF and simple GTR in promoting periodontal bone defect regeneration, and to further explore the efficacy of the three methods in improving the amount of alveolar bone regeneration, so as to provide a basis for future clinical work.

III. Study design

This study is a single-center, simple random parallel group design clinical trial, each random group is allocated according to the proportion of 1:1:1.

IV. Clinical trial site

Responsibilities: Second Affiliated Hospital of Zhejiang University; [name];
[contact];

Address: [name]
Province; [name]

Participation Unit: the Second Affiliated Hospital of Zhejiang University Medical College; person in charge: [name]

V. Design of research

1. Inclusion criteria

(1) Age 18-80 years old; (2) a teeth choice: 6-8 weeks after the teeth after the periodic treatment of teeth, there is at least one site periodontal diagnosis depth (PD) ≥ 5 mm, looseness is less than II The degree or II-III degree will be loose after a fixed fixed, imaging evaluation of the vertical bone absorption of the teeth is greater than 3 mm osteogenesis, and the site is free of teeth surgical treatment, the patient has no obvious symptoms; (3) Patients have better compliance, and the bacterial plaque control is good after the basic treatment (all-in-law bleeding index and the mushroom index), can understand the purpose of testing, willing to cooperate with surgery and follow-up, voluntarily participate in the test and signed Informed consent.

2. Exclusion criteria

(1) In the past 6 months, chewing smokeless tobacco, smoking or suction cigar once a week or more, or smoking more than 20 / week (1 pack / week); (2) patients before blood Three months taking any drug or platelet counts that affect platelet function less than 200,000 / mm³; (3) patients have taken anti-epileptic drugs, antiplasia, antidepressants, sedatives, califiers, anti-depression, sedatives in the

first 1 month before surgery Inflammatory drug or daily analgesic; (4) patients with diabetes history or blood glucose detection abnormal (fasting blood glucose $\geq 7\text{ mmol/L}$); (5) liver, renal function is abnormal (AST, Alt ≥ 1.5 times ULN, creatinine ≥ 1.5 times ULN); (6) has serious endocrine and metabolic diseases; (7) There are historical history of three high blood pressure; (8) History of osteoporosis; (9) History of autoimmune diseases; (10) Because of malignant tumors or other serious medical history, surgery should not be accepted or led to observation of teeth; (11) Pregnancy or lactating women; (12) Patients with anesthetic allergy; (13) Clinical or radiology shows that there are acute infections, root lesions, roots, severe eradications, dental bone rats, non-easy to abrasive, and osteoplasses (CEJ) or There is no treatment of untreated bilrels in the roots, the repair body is gains and / or in CEJ or the following repair edges are not in close; (14) A subject that can cause oral imaging inspection artifacts, such as: The study of teeth and its neighboring teeth are metal dentures, porcelain teeth; (15) a patient with root-stricken lesions;

3. Diagnostic criteria

(1) . Periodontal pocket $> 3\text{ mm}$, and inflammation, gingival bleeding (2) . Adjacent clinical attachment loss $> 1\text{ mm}$ (3) . Periodontal pocket bleeding on probing (4) . Alveolar bone has horizontal or vertical resorption. The progress of the disease is slow, and the teeth are loosened or displaced in the late stage.

4. Criteria for withdrawing / terminating tests

(1) . Any unexpected time to break blindness (2) . Patients who were found to be sensitive to or rejected implants during / after operation. (3) . Problems in need of treatment that met the exclusion criteria. (4) . Patients with irresistible factors such as non-migration / death lost follow-up during the study period.

VI. Research methods

1. Randomized controlled scheme

A simple random method is used for random grouping. The specific method is as follows: first, a column number 1x 78 is established by Excel2013, and then the random number between 0 and 1 is generated by the other column, and then sorted by the largest to the smallest. The first 26 numbers are assigned to the GTR group, the middle 26 numbers are assigned to the APRF+GTR group, and the last 26 numbers are assigned to the CGF+GTR group. The subjects were divided into GTR group, APRF+GTR group and CGF+GTR group according to 1:1:1. (2) researcher A put the implant name (APRF or CGF or none) corresponding to the group mark into 78 Kraft paper envelopes with serial number 1: 78 and opaque according to the distribution order list. A gave the sealed envelope to B and no longer participated in the follow-up study. Researcher B is responsible for including the subjects according to the inclusion criteria, assigning the tested according to the order of seeing a doctor, and is responsible for supervising the operation process.

2. Blind design

Researcher A put the name of the implant corresponding to the group mark (APRF or CGF or none) into 78 Kraft paper envelopes with serial number 1x78 and opaque according to the assigned order list. A gave the sealed envelope to B and no longer participated in the follow-up study. Researcher B is responsible for including the subjects according to the inclusion criteria and assigning the number of the subjects according to the order of seeing a doctor. During the operation, researcher B will hand over the sealed envelope to the surgeon according to the number, supervise the operation process, and do not participate in other studies such as measurement. The survey researcher is responsible for measuring various indicators on a regular basis. Until the end of the experiment, the measurement researchers did not know how the subjects were grouped.

3. Treatment scheme

The newly diagnosed patients were recalled after 6-8 weeks of basic treatment to evaluate whether they met the inclusion exclusion criteria and confirm the operation site. For the patients considering inclusion, they agreed on the operation time one week later (female patients avoided menstruation). Oral health education was given to the patients again. One week later, the operative (V0), the informed consent form was signed by the patient, and then the researchers measured the baseline of the included patients, including (1) clinical periodontal index: probing depth (PD), clinical attachment level (CAL), mobility

(mobility), probing bleeding (BOP). (2) Imaging examination: the height of bone defect (IC), bone level (RBL) and the angle of intraosseous defect were measured by CBCT image, and the volume of intraosseous defect was measured after three-dimensional reconstruction of the affected teeth: all measurements were repeated twice to take the average value; before the actual measurement, all measurement researchers have passed the consistency test. Researcher A uses a random number table for random grouping and uses opaque sealed envelopes for distribution and concealment, and then hands over the envelopes to researcher B and no longer participates in the follow-up study. Researcher B numbered the enrolled patients 1-78 in order. Before the operation, researcher B handed over the sealed envelope to the itinerant nurse to open it, and both the patient and the patient were blind at this time. Since then, researcher B is responsible for supervising the operation. All the operations were performed by experienced surgeons. The surgical area was anesthetized before operation, intraoral and perioral routine disinfection was performed, and the operation was carried out in accordance with the principles of routine periodontal regeneration and aseptic operation.

If the patient was assigned to the APRF+GTR group, 20ml was collected with a blood collection needle from the superficial elbow vein immediately before operation and placed in two special glass centrifuges for APRF. Immediately after the blood collection was completed, the blood was symmetrically placed in the TR-18plu series centrifuge, and the 14min was centrifuged with 1500rpm at room

temperature. After centrifugation, the intravascular blood was divided into three layers: the upper layer was PPP, the middle was yellowish cylindrical gel-like APRF, and the bottom layer was erythrocyte layer. The 2 test tubes completed by centrifugation were placed vertically on the operating compartment table for backup (not tilted or inverted). Simplified gingival papilla retained incision cut full thickness flap and fully relaxed incision and (the flap should be extended 1-2 teeth to the proximal and distal part of the tooth, if the adjacent tooth is missing, the incision should be extended at least 5-10 mm to the area of edentulous teeth). Thoroughly remove the root calculus, plaque and granulation in the defect area with a Gracey curette and spoon, expose the intraosseous defect, cut one piece of APRF gel into 1-2mm particles and mix with Bio-oss, and the other piece is pressed into a 1mm film with special equipment; trim the Bio-gide collagen membrane according to the shape of the bone defect, the membrane should cover the edge of the defect at least 2mm. The mixture of APRF and Bio-oss was filled into the bone defect, the Bio-gide membrane was trimmed, and then the APRF membrane was covered with it; the gingival flap was restored to close the window with improved cross-horizontal mattress suture; periodontal plug agents were placed in the operation area.

If the patient was assigned to the CGF+GTR group, the patient immediately used a blood collection needle from the superficial elbow vein to collect blood about 20ml, which was placed in two special CGF centrifuges with silica coating on the inner wall of the centrifugal tube. Immediately after the blood collection

was completed, the symmetrical Medifuge centrifuge was selected, and the CGF procedure was selected and centrifuged for 13 minutes. The CGF centrifugation procedure is as follows: accelerate for 30 seconds, rise to 2700r/min, centrifuge for 2 minutes, then descend to 2400r/min, centrifuge for 4 minutes, accelerate to 2700r/min, centrifuge for 4 minutes, then descend to 3000r/min, centrifuge for 3 minutes, and decelerate to stop in the last 36 seconds. Finally, the blood in the test tube is divided into three layers: the top layer is PPP, the lowest layer is crimson jelly-like red blood cells and platelets, and the middle layer is yellow translucent gel-like CGF. The 2 test tubes completed by centrifugation were placed vertically on the operating compartment table for backup (not tilted or inverted). The APRF gel in the above process was changed to CGF gel, mixed and covered with CGF, and the other operations were the same.

If the patient was assigned to the GTR group, no blood was drawn. Gel or membrane containing growth factor was not used to cover the operation, and the rest of the operation was the same.

At the end of the operation, the surgeon gave the patient postoperative medical advice and given postoperative medication: cefuroxime axetil 50mg, ornidazole 500mg, twice a day for 5-7 days. Oral hygiene education was given to the patients again, and patients were advised to use Koutai mouthwash twice a day for 2 weeks, and about 2 weeks later to remove stitches. Two weeks after operation, stitches were removed by the original surgeon, and the patients were scheduled for 12 weeks \pm 7 days (V1), 24 weeks \pm 14 days (V2) and 48 weeks \pm 28

days (V3).

VII. Observation index and evaluation of curative effect

The patients were contacted and followed up by researcher B at 12, 24 and 48 weeks after operation. At 12 weeks \pm 7 days after operation, PD, CAL, mobility and BOP were measured by measurement researchers. 24 weeks \pm 14 days and 48 weeks \pm 28 days after operation, the researchers measured PD, CAL, mobility, BOP, RBL, IC, intraosseous defect angle and bone defect volume.

PD (probe depth) :use a periodontal probe (UNC-15,Hu-Friedy,Chicago,IL) paralleling to the long axis of the tooth to measure the distance from the bottom of the periodontal pocket to the gingival margin (mm), record six sites of each tooth (the mesial, median and distal site of the buccal and tongue surface).

CAL (clinical attachment level) : The distance from periodontal pocket bottom to CEJ was measured by periodontal probe (mm). Record six sites of each tooth (the mesial, median and distal site of the buccal and tongue surface).

mobility: use a tweezer to clamp the incisal areas of the anterior teeth or the pit groove on the occlusal surface of the posterior teeth and shake the teeth faciolingually, mesiodistally and vertically. I degree : abnormal mobility faciolingually or less than 1mm positioning. II degree : abnormal mobility faciolingually and mesiodistally or loosening range of 1-2mm. III degree : abnormal mobility faciolingually, mesiodistally and vertically or loosening range is

greater than 2mm.

BOP(bleeding of probe) : observe for 10-15 seconds after probe to see whether it bleeds. Record six sites of each tooth (the mesial, median and distal site of the buccal and tongue surface).

RBL(radiographic bone level): Locate the reference point at the deepest PD site of the affected tooth: cemento-enamel junction (CEJ), alveolar crest (AC), bone defect (BD) .RBL is the straight line distance from CEJ to BD (mm)

IC: IC is the straight line distance from AC to BD (mm)

regenerated bone volume parameters : in mimics software, threshold was set according to the gray value of the affected tooth and its surrounding alveolar bone, image editing and region growth were used to form a mask of the three-dimensional reconstruction area. The three-dimensional calculation function was used to reconstruct the three-dimensional shape of the alveolar bone in the target area. Furthermore, the structure of alveolar bone was optimized by remeshing and smooth. The volume of alveolar bone before and after operation was calculated by Boolean operation to obtain the model of regenerated alveolar bone and its volume was measured.

Defect fill (%) = (preoperative IC- and postoperative IC) / preoperative IC × 100%

Defect resolution (%) = (preoperative RBL- and postoperative RBL) / preoperative RBL × 100%

VIII. Statistical analysis method (statistical software: SPSS25.0)

1) data description: measurement data are described by mean \pm standard

deviation, non-normal distribution data are described by median and percentage (25th 75th percentile)

(2) baseline data are compared with normal distribution by one-way ANOVA test, while measurement data of non-normal distribution are described by Wilcoxon rank sum test.

(3) to compare the curative effect, first of all, the normality and homogeneity of variance of the experimental data were tested. If it obeys normality and homogeneity of variance, one-way analysis of variance (One-Way ANOVA) is used to compare the differences of mean among groups. If there were significant differences, pairwise comparisons were made, and multiple comparisons were made with SNK-q test to analyze and compare the differences between groups. If it does not obey normality and homogeneity of variance, Friedman test is used to compare the mean difference of each group; if there is significant difference, pairwise comparison is made by Wilcoxon Matched-Pairs Sighed Rank test. $P < 0.05$ was used as an index of statistical difference.

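### V.4(2) withdraws randomised patients for sensitivity to or rejection of the implant, and nothing says they are still measured or analysed as randomised

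*Combined protocol and SAP*

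**What the plan says.** Section V.4 gives four criteria for withdrawal or termination. Criterion (1) is "Any unexpected time to break blindness". Criterion (2), the one at issue, is "Patients who were found to be sensitive to or rejected implants during / after operation". Criterion (4) concerns loss to follow-up. The section does not say what happens to a patient's later visits or data once a criterion is met.

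The document does not define *implant*. In Section VI.1 the envelopes carry "the implant name (APRF or CGF or none) corresponding to the group mark", which makes it the randomised component. The background calls APRF "the latest generation of autologous platelet concentrate", and Section VI.3 prepares both APRF and CGF from the patient's own blood. The same operation also places two materials that do not come from that blood. For APRF the instruction is "cut one piece of APRF gel into 1-2mm particles and mix with Bio-oss", and the surgeon must also "trim the Bio-gide collagen membrane according to the shape of the bone defect". The CGF and GTR arms otherwise have the same operation, so all three arms receive Bio-oss and Bio-gide.

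Section VII schedules follow-up at 12, 24 and 48 weeks without saying whether withdrawn patients are included. Section VIII specifies descriptive statistics, one-way ANOVA with SNK comparisons, and rank tests. It names no analysis population and no rule for missing values.

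**The concern.** Withdrawal under V.4(2) happens after allocation and depends on how the patient responded to what was placed in the defect. If *rejected* means graft rejection, the patients removed are likely to be among those with the least bone regeneration, which is what the trial sets out to compare. If withdrawal in practice also ends measurement, the arm means describe only patients who tolerated the material. An arm with more rejections would then lose more of its poor results. With 26 patients per arm, a few such losses can matter. A decision on these patients taken after results are seen would be open to the charge of being data-driven.

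**Working it through.** **1. Is the patient already randomised?** Yes. Under Section VI.3 the envelope is opened before the operation, and V.4(2) applies during or after it. Section VI.2 places the handover of the envelope during the operation. That does not change the answer: patients are numbered on inclusion, each number is tied to an envelope, and blood for the platelet arms is drawn before surgery.

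**2. What data would a withdrawn patient have?** From Section VII:

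| Visit | PD, CAL, mobility, BOP | RBL, IC, defect angle, defect volume |
|---|---|---|
| 12 weeks (V1) | yes | no |
| 24 weeks (V2) | yes | yes |
| 48 weeks (V3) | yes | yes |

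A patient withdrawn before 24 weeks and not measured afterwards has no post-operative bone value, so defect fill, defect resolution and regenerated volume cannot be computed. One-way ANOVA on those outcomes cannot use the patient. Section VIII contains nothing that would bring the patient back in.

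**3. How large could the effect be?** The plan has no figure to reproduce beyond 3 x 26 = 78. It gives no rejection rate, effect size or standard deviation (SD), and names no primary outcome. What follows is an illustration on defect fill.

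Inputs: n = 26 per arm (Section VI.1). Assumed: mean fill f = 0% in dropped failures and m = 50% (range 40-60%) in the others. Let k be the failures dropped from one arm, and d the difference in that number between two arms.

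- All-patient mean of an arm = ((26 - k)m + kf)/26. Mean of those retained = m. The arm is flattered by k(m - f)/26.
- Shift in the contrast = d(m - f)/26, in favour of the arm that lost more, whichever that is.

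| d | m = 40% | m = 50% | m = 60% |
|---|---|---|---|
| 0 | 0 | 0 | 0 |
| 1 | 1.5 | 1.9 | 2.3 |
| 2 | 3.1 | 3.8 | 4.6 |
| 3 | 4.6 | 5.8 | 6.9 |

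With two failures lost in every arm, each arm reads 50% instead of 24 x 50/26 = 46.2%, and the contrast does not move.

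**4. The same in SD units.** With 26 per arm, two-sided 0.05 and an assumed 80% power, the detectable pairwise difference is (1.960 + 0.842) x sqrt(2/26) = 0.78 SD. If 1 to 4 patients are dropped from one arm only and are 1 to 3 SD worse than those retained, that arm is flattered by (1/26) x 1 = 0.04 SD to (4/26) x 3 = 0.46 SD. This is 5% to 59% of 0.78 SD. Power at that difference falls only from 80.0% to 79.2% with one patient lost and to 76.5% with four. The issue is bias far more than power.

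**5. Effect on spread of scoring unmeasured patients at no change.** With 2 of 26 set to 0% fill (p = 2/26), the others at mean 50% and SD s, the arm SD is sqrt((1 - p)s² + p(1 - p)50²). For an assumed s of 20 (15-25) this is 23.4 (19.6-27.5).

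**The case against.** The strongest reply is that the harm is conditional at each step, and most of that reply stands.

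- The document does not say that withdrawn patients leave the analysis, and Section VII schedules follow-up without any exception for V.4. A reader might infer that the plan excludes treatment failures. The text does not support that. It is silent, and the weakness is that nothing keeps them in.
- The contrast is biased only if losses differ between arms. A reader might infer that the rule favours the platelet arms, because Section VI.1 ties *implant* to APRF or CGF. On that reading only those two arms can lose patients. But products made from the patient's own blood are an unlikely main target of a rejection rule. If Bio-oss and Bio-gide are meant, all three arms are exposed and no reason for unequal losses is apparent. The document does not settle which reading applies.
- The English is a rough translation. *Rejected* could mean refusal by the patient, which is a withdrawal after allocation but not a failed result. Sensitivity found during surgery may be only a safety ground.
- A reader might also connect V.4(3), "Problems in need of treatment that met the exclusion criteria", with exclusion (13), "Clinical or radiology shows that there are acute infections", and conclude that post-operative infections are withdrawn too. V.4 does not name infection and (3) may mean other conditions, so the point does not rely on this.
- Every value in the illustration other than the arm size is assumed. Three excess failures would be 3/26 = 11.5% of an arm, and the true rate may be low.

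None of this removes the gap. V.4(2) is a stated rule acting after randomisation on a treatment-related event, and following the plan as written can remove failures from the bone analysis.

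**Conclusion.** The point holds in limited form. V.4(2) can withdraw randomised patients for a treatment-related event, and neither V.4, Section VII nor Section VIII says that they are still measured or analysed in their assigned arm. Because bone outcomes start at 24 weeks, an early withdrawal without further measurement means no bone outcome at all. This can flatter an arm, and it biases a comparison if the losses are unequal. Direction and size cannot be determined from the document. The shifts of about 2 to 6 points for one to three excess losses rest on assumed fill of 0% and 50%, and show only that a few patients could matter at 26 per arm. The conclusion that the lost patients do badly depends on *rejected* meaning graft rejection. The plan should be changed, but this is not evidence that the comparison will be biased.

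**What to change.** Leave clinical management unchanged.

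1. In V.4, state that meeting criteria (1) to (3) does not end outcome measurement, and that the V1-V3 measurements are still taken where the patient consents and the examination is clinically acceptable.
2. In Section VIII, state that the main analysis includes all randomised patients with a measured outcome, in their assigned arm, whether or not they met a V.4 criterion. Add one sensitivity analysis that sets patients without a value to no change from baseline.
3. Define *implant*, saying whether it covers Bio-oss and Bio-gide, and say whether *rejected* means graft rejection or refusal by the patient.
4. Report rejection, sensitivity and withdrawals by arm and reason.

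A fixed failure score in the main analysis, multiple imputation, or a range of assumed failure values could be added, but statisticians would differ on them and they are optional. With 26 per arm and no post-operative bone data before 24 weeks, imputation for an early withdrawal would rest on baseline and clinical indices alone.

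The cost is a few sentences and attendance at visits already scheduled. Arm means may be slightly less favourable and the spread slightly larger, as in step 5 of the working, which lowers power somewhat in the no-change analysis. Scoring at no change may also affect the normality check that selects the test in Section VIII.

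### One researcher enrols and numbers patients, holds all 78 envelopes and supervises surgery, so later allocations on the fixed 26/26/26 list are partly predictable to the enroller; separating the roles is a cheap improvement

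*Combined protocol and SAP*

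**What the plan says.** The design is single-centre with three parallel groups, and "each random group is allocated according to the proportion of 1:1:1" (section III). Section VI.1 opens with "A simple random method is used for random grouping" but then sorts 78 random numbers and cuts the list in three: "The first 26 numbers are assigned to the GTR group, the middle 26 numbers are assigned to the APRF+GTR group". The remaining third goes to the CGF arm.

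The duties of researcher B are spread over several sections:

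- **Enrolment and numbering** (VI.1, repeated in VI.2): "Researcher B is responsible for including the subjects according to the inclusion criteria, assigning the tested according to the order of seeing a doctor".
- **Custody** (VI.1 and VI.2): "A gave the sealed envelope to B and no longer participated in the follow-up study".
- **Theatre** (VI.3, after the envelope is handed over): "Since then, researcher B is responsible for supervising the operation".
- **Follow-up** (VII): "The patients were contacted and followed up by researcher B at 12, 24 and 48 weeks after operation".

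There are safeguards. The envelopes are opaque, sealed and serially numbered. Patients are numbered in order of attendance. B takes no part in measurement, and the measurement researchers stay blind to the end (VI.2). In VI.3, consent and baseline measurement are described before the envelope is handed over.

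The account of the opening is not consistent. VI.2 has B give the envelope to the surgeon during the operation; VI.3 has B give it to the circulating nurse, who opens it beforehand. The source of the random numbers also differs: Excel in VI.1, a random number table in VI.3.

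**The concern.** Concealment protects the comparison when the person who decides whether and when a patient enters cannot foresee the next assignment. Here that person also keeps the envelopes and stands in theatre. The arms are easy to tell apart there: no blood is drawn for GTR, and APRF and CGF use different centrifuges (VI.3). With arm totals fixed, anyone who has seen the earlier assignments can count what is left.

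Eligibility and the operation date are settled about a week before surgery, and some inclusion criteria call for judgement (compliance, plaque control; V.1). A patient could therefore be deferred or reordered. Custody without a log also leaves the envelope order unchecked. Blinded measurement protects the outcome readings but not the selection of patients. The efficacy analysis in section VIII is an unadjusted comparison of groups, so a prognostic imbalance created at entry would pass into the result.

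**Working it through.** **Inputs.** List of 78 with 26 per arm (VI.1): 3 × 26 = 78, which agrees with the number of envelopes. The documents give no accrual rate, standard deviation or target difference, so lag and steering are assumptions and are shown as ranges.

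**1. Predictability with full recall and no lag.** Before patient *i*, let r1, r2 and r3 be the envelopes left in each arm, with r1 + r2 + r3 = 78 − i + 1. The best guess is the arm with most left, and it is right with probability E[max(r1, r2, r3)] / (78 − i + 1). This was computed exactly over all paths of a random 26/26/26 permutation.

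- Patient 1: 33.3%; patient 26: 37.1%; patient 52: 41.0%; patient 70: 49.0%; patient 75: 58.7%; patient 76: 62.4%; patient 77: 66.2%; patient 78: 100%.
- First 52 patients: 19.37/52 = 37%. Last 26: 12.93/26 = 50%. Last ten: 5.94/10 = 59%. Last three: (62.4 + 66.2 + 100)/3 = 76%.
- All patients: 32.3/78 = 41%, against 26/78 = 33% by chance, a gain of 6.3 correct guesses.
- Expected number of assignments known with certainty: 3 × 26/53 = 1.47.

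**2. Scheduling lag.** If *k* patients are booked but not yet operated on when the next one is scheduled, B's knowledge for patient *i* is that of patient *i − k* above.

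- One such patient: last three (58.7 + 62.4 + 66.2)/3 = 62%; the final patient drops from 100% to 66%.
- Three such patients: last three, using patients 73 to 75, (53.1 + 54.8 + 58.7)/3 = 56%; the final patient drops to 59%.

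**3. Bias if B steered.** Assumption: B enters patients who are 0.25 or 0.5 SD better in prognosis when GTR looks unlikely, and equally worse when GTR looks likely. There is no lag and no treatment effect, and the test is one-way ANOVA at 0.05. Two rules bracket the behaviour (simulation, 20,000 lists):

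- *Clear signal only* (chance of GTR at least 50% or at most about 17%): about 10% of patients steered; bias 0.03 SD (0.25 SD shift) to 0.06 SD (0.5 SD shift); rejection 5.3% to 5.5%.
- *Any deviation from 1/3*: about 91% of patients steered; bias 0.07 SD to 0.14 SD; rejection 5.7% to 6.9%.
- *No steering*: rejection 5.1%.

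**4. Which part of the design matters more.** If the enroller neither holds envelopes nor sees assignments, expected correct guesses fall from 32.3 to 26 of 78 and certain ones from 1.47 to 0, with the same list. Changing only the list to small fixed blocks of known size, with B's roles unchanged, makes matters worse: blocks of 3 give 47.7 correct guesses and 26 certain; blocks of 6 give 43.8 and 15.6; blocks of 9 give 41.5 and 11.1.

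**The case against.** The strongest reply is that the plan already has the usual protections: opaque numbered envelopes prepared by someone who then leaves, numbering by attendance, consent and baseline before opening, and blinded measurers. Prediction is weak for two thirds of recruitment, normally only the last one or two assignments are certain, and any lag removes even that. The larger bias figures need deliberate steering of nearly every patient on differences as slight as 34% against 33%. All of this stands, and it limits the size of the point. It does not answer the gap itself: sealed envelopes guard against others, not against a custodian who also enrols and keeps no log.

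A reader might infer more than the documents support:

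- *That concealment has failed or recruitment was steered.* Nothing in the text shows either.
- *That the plan states B knows each arm.* It does not. This is an inference, though a strong one, from supervising visibly different operations.
- *That VI.2 and VII contradict each other on B's role.* VI.2 keeps B out of other work such as measurement. VII gives B the contacts while measurement researchers take the readings. Contact is not measurement, so this is at most a tension.
- *That B's follow-up contact will produce unequal return rates.* A contact who probably knows the arm is undesirable, but the plan does not say who decides withdrawals, and no figure can be put on retention.

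**Conclusion.** The point holds as a cheap improvement, not as a flaw that undermines the trial. One person decides inclusion, numbers patients, holds every envelope and very probably learns each assignment, with no described check on the order or opening of envelopes. That combination is the main weakness. The fixed 26/26/26 list, mislabelled as simple, adds a smaller one.

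Predictability lies between chance (26 of 78, if B recalls nothing) and 32.3 of 78 (full recall, no lag), and is substantial only for roughly the last ten patients. Under assumed steering of 0.25 to 0.5 SD, bias in the platelet-versus-GTR contrast runs from about 0.03 to 0.14 SD depending on how readily B acts, and the false-positive rate stays between about 5% and 7%. These figures exclude tampering with envelopes, which could add to them but cannot be sized from the documents.

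**What to change.** Amend VI.1 to VI.3 (and VII where noted), using existing staff:

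- The circulating nurse, who already opens the envelope in VI.3, holds the envelopes.
- B confirms eligibility and fixes the enrolment number but neither holds envelopes nor attends surgery. A team member who does not enrol or measure supervises the operation. B can then keep the contacts in VII as someone who was not in theatre.
- Do not move eligibility or follow-up contact to the blinded measurement researcher. Patients know whether blood was drawn, and more contact gives the outcome assessor more chances to hear it.
- Release envelopes in serial order, each only after consent, recorded baseline, and the patient number and date written on its outside. Keep an opening log.
- Describe the list as restricted randomisation with fixed totals of 26/26/26, and do not rely on small fixed blocks as the remedy.
- Reconcile VI.2 and VI.3 on who opens the envelope and when, and VI.1 and VI.3 on the source of the random numbers.

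The cost is protocol wording, a simple log and some rearrangement of theatre and screening duties. Sample size and analysis do not change.
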